3.1 Primary Objectives

To determine if exposure to 1 mg of Rasagiline daily is associated with improved regional brain metabolism in the treatment group compared to the placebo group in Alzheimer's Disease patients

3.2 Secondary Objectives

- To evaluate the efficacy of Rasagiline 1 mg once daily compared to placebo after 24 week treatment on cognition (ADAS-cog), activities of daily living (ADCS-ADL), global function (CIBIC+), and neuropsychiatric symptoms (NPI)
- To evaluate the efficacy of Rasagiline 1 mg once daily compared to placebo after 24 week treatment on measures of executive function (mazes and cancellation of the ADAS-Cog13, Digit Span test, and Controlled Oral Word Association Test [COWAT] for verbal fluency)
- To evaluate the safety and tolerability of Rasagiline as measured by incidence of adverse events/serious adverse events (AEs/SAEs) clinical lab test data, vital signs, 12 lead EKG data, brain MRI finding

4 Populations of Interest

- Intent-to-Treat (ITT) Population: All consented randomized subjects grouped according to the treatment assigned at randomization, regardless of any protocol violations or any crossovers.
- Per-Protocol (PP) Populations: All Intent-to-Treat subjects who meet the inclusion criteria and exclusion criteria specified for enrollment in the protocol, and complete the study (week 24), have ingested between 80% and 120% of the protocol prescribed study medication as measured by pill count, and with no protocol violations that affect the analysis.

5 Analyses Populations: Definitions

- FDG Analyses: The primary FDG analysis will include all patients who received both a screening and end of study scan of acceptable quality.
- Clinical Outcome Analyses: The primary clinical analyses will include the ITT population.
- Safety Analyses: The primary clinical analyses will include the ITT population.
- Responder analysis: Responders will be defined as those that have a significant improvement on brain metabolism on FDG for the whole brain or for any of the pre-specified regions.

6 Enrollment and Participant Flow

6.1 Accrual of the study

Tables will summarize accrual by study site, and figures will summarize the overall rate of accrual over calendar time. The observed rate and projected rate of accrual will be displayed in a graph (the projected rate assumes uniform accrual over time).

6.2 Study Flow CONSORT Diagram

A description of participant flow per the CONSORT guidelines (Begg, 1996) will be performed. The diagram will describe study status from screening to the end of the study. At each stage, reasons for persons not moving forward will be summarized by frequency and category for reason. The diagram will include the following information:

- Number of subjects screened
- Number and reason for those who screen failed
- Number of subjects randomized
- Number of subjects who completed the week 24 assessments
- Number and reason for subjects who discontinued study before week 24
- Number of subjects who completed week 28 assessments
- Number and reason for subjects who discontinued study between week 24 and week 28

The CONSORT diagram is separated by study arm after the randomization step.

6.3 Premature Discontinuation of Study Evaluation

Premature discontinuation of the study will be defined as anyone leaving the study and/or discontinuing treatment prior to having a week 24 assessment. Proportions of subjects who prematurely discontinue study treatment within 24 weeks will be compared between the study arms using a Fisher's exact test. In addition, participants who discontinue between 24 and 28 weeks will be reported by study arm and overall. Similar tables and comparisons will be included for participants who prematurely discontinue from the study within 24 weeks. A table will summarize reasons for prematurely discontinuing study between week 24 and week 28 by study arm and overall.

7 Evaluation of Demographics and Baseline Characteristics

Tables will summarize the study population at baseline, overall and by study arm. Descriptive statistics will be presented as N, mean, standard deviation, minimum, 25th Q, median 75th Q and maximum for continuous variables and frequency tables (row, column percentages) for categorical variables. Statistical comparisons will be performed between randomized arms using Wilcoxon Rank Sum Test (for continuous variables) or Fisher's exact test (for categorical variables).

- Baseline Demographics: All variables collected in the Participant Demographics form
- Baseline Medical History: All variables collected in the Medical History Form
- Baseline Vital Signs: All variables collected in the Orthostatic Vital Signs Form
- Baseline Clinical Measures:
 - ADAS-Cog11
 - ADCS-ADL
 - NPI (individual item and total)
 - Digit Span
 - COWAT
 - QoL-AD (Study Partner)

8 Imaging Analysis (Extracted from the protocol)

8.1 Screening Classification

The Screening FDG PET scan of each subject will be evaluated using ADMdx's dementia classifier, to assess whether the subject expresses a pattern consistent with AD or alternatively, that of other dementias. The classifier has developed machine learning methods and a comprehensive set of reference data from ADNI and other sources. The FDG PET scan of a subject will be independently compared to a set of canonical variant patterns that in combination characterize the patterns of relative hypometabolism caused by different types of dementia. A probability will be assigned to determine whether the subject is AD-like or better characterized as a different dementia.

In addition, hypometabolism will be assessed in frontal cortex and occipital cortex, and parietal asymmetry checked, to identify possible atypical or comorbid presentations that may impact clinical attributes. The AD-like or non-AD-like status of each subject will be reported back within 7 days of image receipt to allow enrollment decisions.

8.2 Screening Characterization

The Screening FDG PET scan of each subject will be evaluated using ADMdx's AD Progression classifier, to assess the subject's disease-related hypometabolism status relative to reference subjects and other study subjects. The FDG PET scan of a subject will be independently compared to a set of canonical variant patterns that in combination characterize the patterns of relative hypometabolism caused by different stages of progression toward AD dementia. This numeric score will be used to project likely cognitive trajectory for comparison to actual results. It can also be used to stratify groups for sub-analyses, creating more homogeneous analysis groups at baseline.

8.3 Longitudinal Voxel-Based Evaluation

The spatially normalized longitudinal FDG PET scans of each subject will be analyzed using ADMdx's NPAIRS multivariate software. Classes will be defined according to treatment or placebo condition, and visit. Example analyses are shown in Table 1 below. The output of this evaluation will be a series of patterns showing relative increases and decreases in cerebral glucose metabolism, quantification of the placement of each subject at each time point relative to these patterns of effect, and quantification of the contribution of each pattern to the overall effect. Metrics of reproducibility and predictive power are also provided. At preference of Sponsor, group assignments may be provided in a blinded manner - that is, Group A and Group B, without designation as treatment or placebo. In the table below, to better illustrate the comparisons, they are referred to as Placebo and Treatment, but these may instead be "Group A" and "Group B".

SPM-t contrasts will also be performed of selected groups, at thresholds of $p < 0.005$, and a cluster extent threshold of 25 voxels. These are limited to paired contrasts (e.g. baseline vs. 6 months for treatment group), or to contrasts of the difference images between baseline and 6 months, treatment vs. placebo groups. Information is more limited with regard to individual subject distribution other than at specific voxel locations.

8.4 Longitudinal Region of Interest based Evaluation

The SUVrs calculated for each subject will be compared using t-tests, within groups and across groups, as shown in Table 4 below. While the pre-identified reference regions for testing will be whole brain, cerebellum, and pons, an alternate reference region may be identified through the use of NPAIRS multivariate analysis and applied.

9 Analysis of Clinical Measures

In general, analyses will incorporate the Intent-to-Treat principle, namely, all randomized participants will be included in the analysis. Analyses for all efficacy outcomes will be guided by exploratory analyses. All results will be reported as point estimates (odds ratios or mean differences across groups, as appropriate) and interval estimates (95% confidence intervals) with two-sided p-values denoting statistical significance. Since this is an early phase safety and preliminary efficacy study, no adjustments for multiple comparisons will be made and a p-value of 0.05 will be considered statistically significant.

All clinical measures (MMSE, ADAS-Cog11, ADCS-ADL, NPI, Digit-Span, COWAT and QoL) over 24 weeks will be analyzed using the linear mixed-effects regression model to assess the difference in the rate of change between the two treatment arms. The model will include scores as the dependent variable and time, treatment assignment, time-by-treatment interaction term and any variables determined to be confounders as independent variables. Time will be treated as a continuous variable. An unstructured variance-covariance structure will be used. A significant treatment effect will be concluded if the p-value for the time-by-treatment interaction term in the model is ≤ 0.05 . Sensitivity analyses will be conducted by analyzing the data using response profiles. Here, time will be treated as a categorical variable. The analysis of response profiles will allow us to characterize the patterns of change in the mean response over time in the treatment groups.

To assess the rate of change in the ADCS-CGIC over 24 weeks, a generalized estimating equations (GEE) model for binary data will be used. Because very few change scores were at the extreme ratings of marked worsening, moderate worsening, marked improvement, or moderate improvement are expected in this study, the ADCS-CGIC will be treated as a dichotomous dependent variable (no change/improved and worse).

The analyses will be repeated in the PP population.

10 Correlation between Imaging and Clinical Change

The relationship between FDG-PET measures and change in cognitive endpoints over 24 weeks will be evaluated using a multivariable regression model.

11 Evaluation of Safety Measures

- Event and Participant count of the following will be summarized overall and by treatment group
 - AE: Overall and by MedDRA System Organ Class
 - AE: MedDRA Preferred Term
 - SAE: Overall and by MedDRA System Organ Class
 - SAE: MedDRA Preferred Term
 - SAE Definitely Related to Study Drug: Overall and by System Organ Class
 - Hospitalization
 - Deaths
- Comparisons of the number of participants with at least one AE, SAE, SAE definitely related to study drug and Death will be done between treatment groups using the Fisher's Exact test.
- Change in vital signs (blood pressure, weight, pulse, temperature) will be compared between treatment group using the Wilcoxon Rank-Sum test

12 Software

Statistical software R (version 3.1.1) will be used <http://www.r-project.org>.

13 References

Begg, et al. (1996). Improving the quality of reporting of randomized controlled trials: The CONSORT statement, JAMA, 276(8), 637-639

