11.2 Statistical Methods

Intent-to-Treat (ITT) - The primary FDG analysis will include all patients who received both a screening and end of study scan of acceptable quality. The primary clinical analysis will be a modified Intent-to-Treat (mITT) approach including all patients randomized and receiving at least one post-baseline assessment.

Per-Protocol (PP) population – All Intent-to-Treat subjects who complete the study (Week 24) and have ingested between 80% and 120% of the protocol prescribed study medication as measured by pill count.

Observed case – An observed case analysis of all patients completing the study will be conducted.

LOCF – Clinical data imputation will use the LOCF approach for missing patients

Responder analysis – Responders will be defined as those that have a significant improvement on brain metabolism on FDG for the whole brain or for any of the pre-specified regions.

A secondary analysis will compare the changes in FDG at 6 months compared to the projected expected metabolism based on the Baseline FDG findings.

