11.3 Subject Populations for Analysis

With a subject population of 10 patients per arm (placebo and treatment), Kadir et al detected a significant increase ($p < 0.05$) in frontal, parietal, and parietotemporal glucose metabolism within the treatment group, and a significant difference between placebo and treatment arms in parietotemporal glucose metabolism (26). The percent changes associated with these increases ranged from 5.5% to 8%. In two different studies of donepezil (27, 28), the change in glucose metabolism was measured in subjects who improved, rather than declined, in cognitive scores. Using region of interest analysis, Shimadai found significant differences ($p < 0.05$) in frontal regions when comparing the ratio of pre-treatment to post-treatment in 7 responders with regard to ADAS-J cog score to that of 4 non-responders. Using voxel-based analyses, Mega et al found a significant difference in anterior cingulate, prefrontal cortex, and parietotemporal cortex between

6 cognitive responders as compared to similar untreated subjects, even after applying a Bonferroni correction for random effects.

Evaluation of the FDG PET scans of 70 mild AD subjects from the Alzheimer's Disease Neuroimaging Initiative (ADNI) database indicates that, based upon mean and standard deviation of glucose metabolism in prefrontal cortex, a change in mean Standardized Uptake Value ratio (SUVr) of 5% could be statistically significant between two independent groups (drug, placebo) at 70% power ($p < 0.05$, two-tailed) with 26 subjects per arm, or at 80% power with 32 subjects per arm. The number of subjects required reduces quickly with effect, as a change of 10% would require only 8 subjects per arm to achieve 80% power if variance within the study group is comparable to that within the mild AD ADNI population (greater variance would increase the number of subjects required or decrease the power). Region of interest evaluation is typically more conservative than voxel-based analysis because effects common across subjects often involve sub-regions and measurement of change may be diluted by the use of broader pre-determined measurement areas. Use of voxel-based approaches, and in addition, multivariate methods and a pattern-based classification approach, are expected to increase statistical power as they improve the signal to noise ratio and are not limited to predefined regions.

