11.4.4 Longitudinal Region of Interest Evaluation

The SUVr calculated for each subject will be compared using t-tests, within groups and across groups, as shown in Table 4 below. While the pre-identified reference regions for testing will be whole brain, cerebellum, and pons, an alternate reference region may be identified through the use of NPAIRS multivariate analysis and applied.

Table 4 Regions of interest for FDG analysis

Analysis	Change in FDG PET measure:	Dorso-lateral PFC	Striatum	Hip - Med temp	Anterior cingulate	Post cing-precun	Lateral temp	Inferior parietal
1	Treatment: 6m vs. screening	x	x	x	x	x	x	x
2	Placebo: 6m vs. screening	x	x	x	x	x	x	x
3	Change in treatment vs. change in placebo groups	x	x	x	x	x	x	x
4	1, 2, and 3 in substrata for	x	x	x	x	x	x	x

Analysis	Change in FDG PET measure:	Dorso-lateral PFC	Striatum	Hip - Med temp	Anterior cingulate	Post cing-precun	Lateral temp	Inferior parietal
	disease severity and age							

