ADMdx has developed and will utilize an automated image processing pipeline, PETMAX™, which has secure user access, version control with back-up, and complete audit trail for use in clinical trials. PETMAX facilitates user interaction for visual inspection and quality control at multiple stages in the pipeline, and

streamlines the execution of the many steps (including SPM functions) employed in image preparation and analysis. Results are logged and saved under version control.

(ii) Image Processing

Discrete timeframes for each scan will be aligned and an aggregate image created by averaging the frames. Each subject's MRI will be co-registered to the baseline PET scan, and longitudinal PET scans will be co-registered to the baseline PET scan, as well. The MRI will be segmented into gray, white, and CSF tissue images. The MRI will be spatially transformed to a target template and the PET scan(s) will be likewise transformed using the same parameters. The spatially transformed images will be intensity normalized to a mean value of 1, and smoothing applied to achieve uniform resolution with other scanners for comparison to reference data and use in the dementia classifiers. A set of template ROIs will be transformed back to the subject's native (unwrapped) brain for signal measurement in unwrapped space, with individualized masking applied using the subject's gray matter segment. The mean, standard deviation, minimum, and maximum for each ROI will be measured, as well as those in different reference regions for comparison, including whole brain without ventricles, cerebellum, and pons. This is in order to examine consistency across reference regions, and to determine whether treatment effects may influence one or more reference regions as well as target ROIs. Standardized Uptake Value Ratios (SUVrs) will be generated by taking the ratio of regions of interest to the respective reference regions.

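### The between-arm t-test on SUVr change is valid but fixes the screening slope at 1; at the full sample size, ANCOVA on the screening SUVr is a nearly free gain in precision

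*SAP*

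**What the plan says.** SAP 8.4 states "The SUVrs calculated for each subject will be compared using t-tests, within groups and across groups" and protocol 11.4.4 says the same. The SAP points to a Table 4, which is printed in protocol 11.4.4. There, analysis 3 is "Change in treatment vs. change in placebo groups" in each of seven regions, and analysis 4 repeats "1, 2, and 3 in substrata for" disease severity and age. No covariate is named for SUVr in either document. Adjustment for confounders appears only in SAP section 9, in the mixed model for the clinical measures.

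The screening value is available for everyone analysed. SAP section 5 says "The primary FDG analysis will include all patients who received both a screening and end of study scan of acceptable quality". Protocol Appendix A says that SUVrs "will be generated by taking the ratio of regions of interest to the respective reference regions", so a screening SUVr exists for the same region and reference region as each Week 24 SUVr.

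The plan uses the screening scan in other ways. Protocol 11.2 has a secondary comparison with the "projected expected metabolism based on the Baseline FDG findings", and SAP 8.2 allows sub-analyses stratified by the progression score. The voxel-based between-arm contrasts in SAP 8.3 use difference images. None of these adjusts the regional between-arm contrast for the screening SUVr.

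**The concern.** A t-test on change is a linear model for Week 24 SUVr in which the coefficient of screening SUVr is set to 1. If the true coefficient is lower, as regression to the mean usually makes it, the change score over-corrects for screening differences and carries avoidable variance. ANCOVA estimates the coefficient from data the trial already collects.

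Analysis 3 is the regional form of the primary objective, a comparison with placebo. The trial enrols 25 per arm, against the protocol's own 26 per arm for 70% power and 32 for 80%, and withdrawals are not replaced (protocol 5.5). Precision that needs no extra patients is worth having.

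**Working it through.** **Inputs from the documents.** Protocol 11.3 gives a two-sided 0.05 level; for a 5% SUVr difference, 26 per arm at 70% power and 32 at 80%; for a 10% difference, 8 per arm at 80%. Planned size is 25 per arm. The SD is not printed; it is described as "based upon mean and standard deviation of glucose metabolism in prefrontal cortex".

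**Step 1: reproduce the plan's figures.** Solving the noncentral t for the standardised effect gives 0.7026 (26 per arm, 70%) and 0.7115 (32 per arm, 80%). The implied SD is 5/0.7026 = 7.12% and 5/0.7115 = 7.03% of the mean. With SD 7.1%, the normal approximation gives 25, 32 and 8 per arm against the stated 26, 32 and 8, so the figures agree with each other. I use 7.03%.

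**Step 2: compare the two estimators.** Work in units of the screening SD, with k = SD at Week 24 / SD at screening, and rho the correlation between scans. Both k and rho are assumptions.

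- Change score: Var = 1 + k² − 2·rho·k
- ANCOVA residual: Var = k²(1 − rho²), with slope rho·k
- The first minus the second is (1 − rho·k)², which is zero only when the slope is exactly 1.
- Average cost of estimating the slope: a factor 1 + 1/(2n − 4) = 1 + 1/46 = 1.0217 at n = 25 per arm. Residual degrees of freedom go from 48 to 47.

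So the variance ratio (ANCOVA / change) can never exceed 1.0217 at 25 per arm. With k = 1 it is 1.0217·(1 + rho)/2, which equals 1 at rho = 2/1.0217 − 1 = 0.957.

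| rho | ratio, k = 1 | equivalent t-test n per arm (25/ratio) | ratio, k = 1.1 | ratio, k = 0.9 |
|---|---|---|---|---|
| 0.5 | 0.766 | 32.6 | 0.835 | 0.682 |
| 0.7 | 0.868 | 28.8 | 0.941 | 0.767 |
| 0.8 | 0.920 | 27.2 | 0.989 | 0.805 |
| 0.9 | 0.971 | 25.8 | 1.021 | 0.828 |

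In simulation (20,000 trials per setting, rho 0.5 to 0.98), type I error was 4.8% to 5.7% for the t-test and 4.9% to 5.6% for ANCOVA. Both tests hold their level.

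**Step 3: power, if 7.03% is the SD of SUVr level.** This is how protocol 11.3 describes it. With k = 1 and 25 per arm, t-test → ANCOVA:

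| rho | power for 5% | power for 2.5% | 95% CI half-width, % of mean |
|---|---|---|---|
| 0.5 | 69% → 80% | 23% → 29% | 4.0 → 3.5 |
| 0.7 | 89% → 93% | 36% → 40% | 3.1 → 2.9 |
| 0.8 | 97% → 98% | 50% → 53% | 2.5 → 2.4 |
| 0.9 | no change | 79% → 80% | 1.8 → 1.8 |

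On this reading the planned t-test itself reaches 80% power for a 5% difference at rho of about 0.61.

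**Step 4: power, if 7.03% is instead the SD of change.** The t-test has 69.3% power for 5% at every rho. ANCOVA has 80%, 75%, 73% and 71% at rho 0.5, 0.7, 0.8 and 0.9, and 68.3% in the worst case (slope exactly 1). With equal SDs this reading implies a level SD of 7.03/√(2(1 − rho)), which is 11% of the mean at rho 0.8 and 16% at 0.9. That departs from the protocol's description.

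**Step 5: the analysis 4 strata.** Their sizes are not stated, so these are assumed. The same factor 1 + 1/(2n − 4) gives:

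| n per arm | factor | break-even rho (k = 1) |
|---|---|---|
| 12 | 1.05 | 0.905 |
| 8 | 1.083 | 0.85 |
| 5 | 1.167 | 0.71 |

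At rho 0.9 on the level reading, power for 5% falls from about 84% to 83% with 8 per arm, and from about 60% to 54% with 5 per arm.

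**The case against.** The strongest reply is that nothing is broken. The t-test on change is valid, it matches an endpoint defined as change, and choosing between two valid estimators is a preference. The first two statements are right. A reader might infer that the planned test is biased or inflates error; the documents do not support that, and the simulated error rates contradict it. The case for ANCOVA is precision alone.

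Second, the size of the gain is unknown. Ratios in the table run from 0.68 to 1.02. Appendix A asks for the same time of day and consistent uptake conditions across a subject's scans, and prefers no scanner upgrades. These steps should raise rho, where the gain shrinks. This stands, and it is why only a range can be given.

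Third, a reader might infer that ANCOVA closes the gap between 25 and 32 per arm. That is too strong. On the protocol's own description of the SD, power for 5% is below 80% only when rho is under about 0.61. Above that there is no shortfall to recover.

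Fourth, it is tempting to carry the same model into analysis 4. Nothing supports an even split of the strata, and Step 5 shows that small strata can lose power at high rho. This objection stands in full.

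Fifth, Table 4 has seven regions, several reference regions are allowed and no single primary region is named, so power for one test is not the whole picture. This is true, and ANCOVA does not change it, but it does not argue against a more precise estimate in each region.

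**Conclusion.** This is a free improvement at the full sample size, not the correction of an error. Assuming equal SDs at the two scans and 25 analysed per arm, adjusting analysis 3 for the screening SUVr cuts variance by about 23%, 13%, 8% and 3% at rho 0.5, 0.7, 0.8 and 0.9, and gains nothing above about 0.96. If the Week 24 SD is 10% larger, the gain is almost nil from rho 0.8 upward; if 10% smaller, it is larger throughout the range shown. The loss is bounded at about 2% of variance. Above rho of about 0.61 the benefit, on the level-SD reading, is a narrower interval and more power for effects smaller than 5%. The bound on the loss rests on 25 analysed per arm and a single common slope per region; it rises slightly with losses (at 20 per arm, 1 + 1/36 = 1.028). The conclusion does not extend to the analysis 4 strata.

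**What to change.** In SAP 8.4, for Table 4 analysis 3 only, write before unblinding:

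> *Week 24 SUVr will be analysed by ANCOVA with treatment and the screening SUVr of the same region and reference region; the adjusted difference will be reported with its 95% CI.*

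Keep the t-test on change as a sensitivity analysis, and make the matching edit in protocol 11.4.4. Leave analysis 4 as it is.

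The cost is a sentence or two in a SAP still marked as a draft, one line of R code per region, and one degree of freedom. No new data are needed. In the worst case about one point of power is lost (69.3% to 68.3% in Step 4).

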3.4 Secondary Endpoints

- Change from Baseline ¹⁸F-AV-1451 Tau PET imaging SUV_r results to Week 24 results
- Change from Baseline to Week 24 on the scores of MMSE, ADAS-Cog 11, CGIC
- Change from Baseline to Week 24 on the scores of NPI and ADCS-ADL
- Change from Baseline to Week 24 on the scores of Digit Span test, COWAT and QoL-AD/Study Partner
- Safety and tolerability as measured by incidence of adverse events/serious adverse events (AEs/SAEs) clinical lab test data, vital signs, 12-lead EKG data
- Proportion of subjects with adverse events, serious adverse events and adverse events leading to discontinuation over the 24-week double blind treatment period
- Proportion of subjects with laboratory abnormalities
- Proportion of subjects with ECG abnormalities

[figure not shown]

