8.2 Clinical and Functional Evaluations

8.2.1 Clinician Global Impression of Change (CGIC)

This is a rating scale of global impression of change. The CGIC is a clinician assessment of change in the patient's functioning administered to the patient and the caregiver. This test will be conducted at Baseline, Week 4, Week 24, and Week 28.

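### The SAP targets a rate of change in the CGIC, which is already a change rating, without naming the tested term; on its likeliest reading the test is weak against a benefit held from Week 4 to Week 24

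*SAP*

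**What the plan says.** SAP section 9 (Analysis of Clinical Measures) gives the global rating its own short paragraph. The aim is "To assess the rate of change in the ADCS-CGIC over 24 weeks", and for this "a generalized estimating equations (GEE) model for binary data will be used", with the rating split into worse versus no change or improved. The paragraph gives no model terms, no coding of time, no tested coefficient and no statement on whether the Baseline record enters as an outcome.

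The paragraph before it covers seven other measures with a linear mixed model. There, a difference between arms in the rate of change is judged by one term: "A significant treatment effect will be concluded if the p-value for the time-by-treatment interaction term in the model is" at or below 0.05. The categorical-time sensitivity analysis is described with that model, and the CGIC is not among the measures listed.

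Protocol section 8.2.1 says of the CGIC: "This is a rating scale of global impression of change". On timing it says: "This test will be conducted at Baseline, Week 4, Week 24, and Week 28". The Schedule of Activities (Table 2) agrees and shows no Week 8 rating. Protocol section 3.4 gives the endpoint as "Change from Baseline to Week 24 on the scores of MMSE, ADAS-Cog 11, CGIC".

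**The concern.** Each CGIC score already expresses change. For such a scale, the protocol's Baseline-to-Week-24 endpoint is most naturally the Week 24 rating itself. A rate of change in that rating is one step further on: with two post-baseline visits, it is how far the rating moved between Week 4 and Week 24. Compared between arms, it measures whether the treatment effect grew or shrank over that interval, not whether fewer patients on drug are worse at Week 24.

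The CGIC is the only measure of global function among the protocol's secondary objectives (section 3.2). If the interaction is the test, a global benefit present early and maintained could be reported as no treatment effect. No Week 24 CGIC contrast is specified elsewhere in the SAP to correct that impression.

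**Working it through.** **1. Inputs.** From the documents: 25 per arm (Protocol section 4); scheduled ratings at Weeks 4 and 24 within the window (Protocol section 8.2.1, Table 2); binary coding and a two-sided 0.05 level (SAP section 9). The documents give no CGIC rate, effect size or power, so there is no figure to reproduce. Assumed: placebo 'worse' rates of 25-30% at Week 4 and 45-50% at Week 24. Odds ratios below are odds of 'worse' on placebo divided by odds on drug, so values above 1 favour drug.

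**2. What each test estimates.** Let L4 and L24 be the log odds ratios at Weeks 4 and 24. The interaction with continuous time is (L24 − L4)/20 per week. The Week 24 contrast is L24. If the odds ratio is constant, L24 − L4 = 0 whatever its size.

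**3. Constant odds ratio, by hand.** The variance of a log odds ratio at one visit is the sum over arms of 1/[n p(1 − p)], and power in favour of drug is Φ(effect/SE − 1.960).
- Odds ratio 4, placebo 50% at Week 24: drug odds are 1/4, so 20%. Variance = 1/(25 × 0.50 × 0.50) + 1/(25 × 0.20 × 0.80) = 0.160 + 0.250 = 0.410; SE 0.640. ln 4 = 1.386 and 1.386/0.640 = 2.165. Power Φ(0.205) ≈ 58%.
- Odds ratio 3, same placebo rate: drug 25%. Variance = 0.160 + 0.213 = 0.373; SE 0.611. 1.099/0.611 = 1.798. Power Φ(−0.162) ≈ 44%.
- Interaction in both cases: Φ(0 − 1.960) = 2.5%.

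Simulations over the assumed rates give about 2-3% for the interaction and roughly 36-60% for Week 24. Part of that width comes from empty cells. A drug-arm Week 4 rate of 12.5% (placebo 30%, odds ratio 3) gives no 'worse' rating in 0.875^25 ≈ 4% of trials. A rate of 7.7% (placebo 25%, odds ratio 4) does so in 0.923^25 ≈ 13%. The result then depends on how such trials are handled.

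**4. Growing benefit.** Take placebo rates of 30% then 50%, and a within-patient correlation r = 0.25 between the binary ratings (an assumption).
- Odds ratio 1 then 4: the Week 4 variance is 2/(25 × 0.30 × 0.70) = 0.381. The effect is 1.386 for both tests. The covariance factor is √(0.1905 × 0.160) + √(0.1905 × 0.250) = 0.393. Interaction variance = 0.410 + 0.381 − 2 × 0.25 × 0.393 = 0.595; SE 0.771. Power Φ(1.797 − 1.960) ≈ 44%, against 58% for Week 24. Simulation: about 40% versus 54%.
- Odds ratio 1.5 then 4: drug rate at Week 4 is 22.2%. The effect for the interaction falls to ln(4/1.5) = 0.981. Week 4 variance is 0.422, covariance factor 0.415, interaction variance 0.410 + 0.422 − 0.208 = 0.624; SE 0.790. Power Φ(1.241 − 1.960) ≈ 24%, against 58%. Simulation: about 21% versus 55%.

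**5. Fitted GEE simulations.** Logit link, independence working correlation, robust SE, 25 per arm, latent correlation 0.5, no dropout, 1,000 runs per row; percent two-sided rejection. The figure after the slash has Baseline entered as 'no change' for everyone.

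| Assumed 'worse' rates | Interaction | Week 24 contrast | Treatment main effect, no interaction in model |
|---|---|---|---|
| 50% vs 20%, steady | 4.1 / 9.0 | 60.2 / 64.3 | 81.1 / 80.5 |
| 60% vs 20%, steady | 4.8 / 15.4 | 84.9 / 87.4 | 95.7 / 95.6 |
| Placebo 30% to 50%, constant odds ratio 4 | 3.8 / 5.9 | 60.3 / 62.2 | 72.5 / 72.3 |
| Placebo 20% to 60%, drug flat at 20% | 59.2 / 66.7 | 84.9 / 82.9 | 50.6 / 48.9 |

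Under no effect, the interaction without Baseline rejects in 4.7% of runs, so the 4-5% in the steady rows is type I error. The Week 24 contrast is the only one of the three that holds up in all four rows.

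**The case against.** A reader might infer that the SAP prescribes the interaction for the CGIC and that the planned test therefore has no power. The documents do not support either step.

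- **The test is not stated.** The rule that an effect is concluded from the time-by-treatment term belongs to the mixed model, for seven named measures that do not include the CGIC. The same section says results will be reported as odds ratios or mean differences across groups, which would fit a plain between-arm CGIC odds ratio. If a treatment main effect in the same GEE was meant, a steady benefit would be detected (73-96% in the steady rows above), more often than by the Week 24 contrast.
- **Chance-level power belongs to one pattern.** It needs a benefit already full at Week 4, when patients have had only the 0.5 mg step. Protocol section 1.5 allows for disease modification as well as symptomatic benefit, so a growing effect is equally within the rationale.
- **The Baseline record is unsettled.** Neither document says how a Baseline CGIC is scored or whether it enters the model. If it enters as 'no change' for all, a little of a steady benefit reaches the slope.
- **The stakes are limited.** This is one of many unadjusted secondary measures in a 50-patient proof-of-concept trial with an imaging primary endpoint.

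All four stand as limits on the claim. They do not remove it. The only meaning the SAP gives to a difference in rate of change is the interaction, and no other CGIC contrast is named. The interaction was weaker than the Week 24 contrast in every scenario simulated. That ordering is not a theorem: with no effect at Week 4, the interaction would match Week 24 once the correlation between binary ratings reached about 0.381/(2 × 0.393) ≈ 0.49.

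**Conclusion.** The concern holds in conditional form. What is certain from the text is that the SAP names a target, rate of change, that does not match the protocol's Baseline-to-Week-24 CGIC endpoint, and leaves the model terms and tested coefficient open. What is inferred is that the test would be the time-by-treatment interaction.

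On that reading, power against a benefit constant on the odds scale is at chance level when only Weeks 4 and 24 enter. It stays low, at 6-15% two-sided rejection against 62-87% for the Week 24 contrast, if Baseline is entered as 'no change'. For a growing benefit the test is usable but weaker.

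The sizes rest on assumed 'worse' rates, assumed within-patient correlation, 25 evaluable patients per arm and no dropout. The zero interaction under a constant odds ratio, without Baseline, rests on none of these. This should be corrected, but it does not touch the primary endpoint.

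**What to change.** In SAP section 9, replace the rate-of-change wording for the CGIC with a named estimand: the between-arm odds ratio for 'worse' at Week 24, with its 95% confidence interval. Estimate it from a binary GEE with visit (Weeks 4 and 24, categorical), treatment and visit-by-treatment. State that the Week 24 treatment contrast is the test, that the Week 4 contrast is supportive, and that the Baseline record is not an outcome. This matches the endpoint in Protocol section 3.4.

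The cost is a sentence or two in a SAP still marked as a draft. No visit, assessment or patient is added. The change should be made before treatment codes are seen.
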